13.4 Visit 2: CRCLM surgery, Treatment Assessments and Data Collection

Participants will have a trial visit during admission on the first day of the hospital inpatient stay for CRCLM surgery. The CRCLM surgery should be <6 weeks from post randomisation.

The following assessments will be carried out:

- Toxicity assessment: collection of any adverse events which may have occurred since the last research nurse telephone call.
- Details of hospital resource activity (e.g. hospital inpatient stays, outpatient clinics attending, accident and emergency attendances).
- Participant self-reported assessments: a health economics questionnaire will be administered to the participant in a Participant Questionnaire Visit 2 Pack. It is preferable that this is administered to the participant before surgery but if this is not possible within the timeframe pre-surgery, the Visit 2 Pack may be completed during the inpatient stay.
- Participants should be provided with a Participant Diary Booklet to record information over the next visit period. The information collected in the booklet will be the information to be collected in the health economics questionnaire and details on compliance and adverse events. The booklet is intended to act as a reminder to the participant and must not be handed in to clinic or returned to the CTRU.
- Weight in kilograms (in light indoor clothing and without shoes). This may be taken from the pre-operative assessment in the clinical records.
- Blood sample for red blood cell fatty acid analysis (for Sheffield Teaching Hospitals NHS Foundation Trust and Leeds Teaching Hospitals NHS Trust only). **Please note that it is preferable that the blood sample is obtained prior to surgery, ideally on admission to hospital.** A blood sample should be collected in two EDTA-coated Vacuette® tubes and agitated immediately to prevent clotting. The blood components should be separated within 30 minutes of taking the blood sample (see Section 13.16). If not processed immediately, store the two tubes in the fridge at 4°C for up to 30 minutes.
- See Biospecimen Collection protocol if participant is in this sub-study.
- Treatment compliance: the participant will be asked if they have missed any treatment doses since the last research nurse telephone call and for what reason.
- Details of concomitant medications including over-the-counter O3FA supplements since the last research nurse telephone call. Participants should be reminded that over-the-counter O3FA supplements are prohibited.
- The IMP dispensed at visit 1 should be checked regarding the expiry date and the participant should be advised to use the IMP box currently in use before opening the IMP box dispensed at visit 2.
- One box of IMP should be dispensed if necessary.

- **In the event that the liver metastases are not able to be removed surgically and macroscopic disease remains, a CT scan should be arranged as soon as possible in order to measure the existing disease. Trial treatment and follow-up should continue as per protocol.**

13.5 Visit 3: Treatment Assessments and Data Collection

Participants will have a trial visit 6 months +/- 2 weeks after the date of CRCLM surgery. For those participants having adjuvant chemotherapy the CT scan may be during the chemotherapy treatment period to ensure that the trial visit at 6 months +/- 2 weeks can be adhered to. For all participants the following assessments will be carried out:

- Clinical evaluation to assess for disease progression and new primary cancer, as per local standard practice.
- Toxicity assessment: collection of any adverse events which may have occurred since the last trial visit.
- Details of hospital resource activity (e.g. hospital inpatient stays, outpatient clinics attending, accident and emergency attendances).
- Participant self-reported assessments: the EQ-5D, EORTC QLQ-C30 and QLQ-LMC21 Quality of Life questionnaires and a health economics questionnaire will be administered to the participant in a Participant Questionnaire Visit 3-10 Pack. Questionnaires should be completed by participants at the time of clinical assessment, but before discussion of the outcome of any medical assessments or blood tests wherever possible.
- Participants should be provided with a Participant Diary Booklet to record information over the next visit period. The information collected in the booklet will be the information to be collected in the health economics questionnaire and details on compliance and adverse events. The booklet is intended to act as a reminder to the participant and must not be handed in to clinic or returned to the CTRU.
- Weight in kilograms (in light indoor clothing and without shoes).
- CT scan of thorax, abdomen and pelvis.
- Treatment compliance: the participant will be asked if they have missed any treatment doses since the last trial visit and for what reason.
- Details of concomitant medications including over-the-counter O3FA supplements since the last trial visit. Participants should be reminded that over-the-counter O3FA supplements are prohibited.

- Blood sample for red blood cell fatty acid analysis (for Sheffield Teaching Hospitals NHS Foundation Trust and Leeds Teaching Hospitals NHS Trust only). A blood sample should be collected in two EDTA-coated Vacuette® tubes and agitated immediately to prevent clotting. The blood components should be separated within 30 minutes of taking the blood sample (see Section 13.16). If not processed immediately, store the two tubes in the fridge at 4°C for up to 30 minutes.
- See Biospecimen Collection protocol if participant is already in this sub-study.
- If the EMT2 participant has not already taken part in the Biospecimen Collection, an invitation to join the Biospecimen Collection sub-study to provide a single stool and urine sample should be extended to the participant using the dedicated post-surgery PIS/ICF (see Biospecimen Collection protocol).
- If new written informed consent for the Biospecimen Collection sub-study is obtained, a sample collection pack should be provided according to the Biospecimen Collection protocol.
- One box of IMP will be dispensed.
- The IMP dispensed at visit 2 should be checked regarding the expiry date and the participant should be advised to use the IMP box currently in use before opening the IMP box dispensed at visit 3.

For Visit 3 and all subsequent trial visits, follow-up can be on a remote basis by telephone interview, QoL questionnaires posted and courier delivery of IMP, if participants are unable to attend the recruiting hospital for repeat visits. Clinical evaluation, toxicity assessment, compliance and concomitant medication assessment, as well as determination of hospital resource activity, will be performed by telephone. Self-reported weight will be obtained. IMP will be delivered to the participant's postal address (see Section 11.3). CT scanning will be performed by the local Oncology team as per usual surveillance guidelines. Participants randomised in Leeds and Sheffield, but undergoing remote follow-up, will not be expected to provide blood samples for Visit 3.

13.6 Visits 4-6: Treatment Assessments and Data Collection

Participants will have a trial visit at 12, 18 and 24 months (+/- 2 weeks) after the date of CRCLM surgery. The following assessments will be carried out at each visit:

- Clinical evaluation to assess for disease progression and new primary cancer, as per local standard practice.
- Toxicity assessment: collection of any adverse events which may have occurred since the last trial visit.

- Details of hospital resource activity (e.g. hospital inpatient stays, outpatient clinics attending, accident and emergency attendances).
- Participant self-reported assessments: the EQ-5D, EORTC QLQ-C30 and QLQ-LMC21 Quality of Life questionnaires and a health economics questionnaire will be administered to the participant in a Participant Questionnaire Visit 3-10 Pack. Questionnaires should be completed by participants at the time of clinical/telephone assessment, but before discussion of the outcome of any medical assessments or blood tests wherever possible.
- Participants should be provided with a Participant Diary Booklet to record information over the next visit period. The information collected in the booklet will be the information to be collected in the health economics questionnaire and details on compliance and adverse events. The booklet is intended to act as a reminder to the participant and must not be handed in to clinic or returned to the CTRU.
- Weight in kilograms (in light indoor clothing and without shoes).
- CT scan of thorax, abdomen and pelvis.
- Treatment compliance: the participant will be asked if they have missed any treatment doses since the last trial visit and for what reason.
- Details of concomitant medications including over-the-counter O3FA supplements in since the last trial visit. Participants should be reminded that over-the-counter O3FA supplements are prohibited.
- One box of IMP will be dispensed.
- The IMP dispensed at the previous visit should be checked regarding the expiry date and the participant should be advised to use the IMP box currently in use before opening the IMP box dispensed at this visit/telephone call.
- See Biospecimen Collection protocol if participant is already in this sub-study. A sample collection pack may need handing /posting to the participant at visit 5.
- If the EMT2 participant has not already taken part in the Biospecimen Collection, an invitation to join the Biospecimen Collection sub-study to provide a single stool and urine sample should be extended to the participant using the dedicated post-surgery PIS/ICF (see Biospecimen Collection protocol).
- If new written informed consent for the Biospecimen Collection sub-study is obtained, a sample collection pack should be provided according to the Biospecimen Collection protocol.

See Section 13.5 for details of remote follow-up for Visits 4-6.

13.7 Visits 7-9: Treatment Assessments and Data Collection

Participants should have a trial visit at 30, 36 and 42 months (+/- 2 weeks) after the date of CRCLM surgery. The following assessments will be carried out at each visit:

- Clinical evaluation to assess for disease progression and new primary cancer, as per local standard practice.
- Toxicity assessment: collection of any adverse events which may have occurred since the last trial visit.
- Details of hospital resource activity (e.g. hospital inpatient stays, outpatient clinics attending, accident and emergency attendances).
- Participant self-reported assessments: the EQ-5D, EORTC QLQ-C30 and QLQ-LMC21 Quality of Life questionnaires and a health economics questionnaire will be administered to the participant in a Participant Questionnaire Visit 3-10 Pack. Questionnaires should be completed by participants at the time of clinical assessment, but before discussion of the outcome of any medical assessments or blood tests wherever possible.
- Participants should be provided with a Participant Diary Booklet to record information over the next visit period. The information collected in the booklet will be the information to be collected in the health economics questionnaire and details on compliance and adverse events. The booklet is intended to act as a reminder to the participant and must not be handed in to clinic or returned to the CTRU.
- Weight in kilograms (in light indoor clothing and without shoes).
- CT scan of thorax, abdomen and pelvis at visit 8 only: CT scans are carried out on an annual basis after 2 years post CRCLM surgery.
- Treatment compliance: the participant will be asked if they have missed any treatment doses since the last trial visit and for what reason.
- Details of concomitant medications including over-the-counter O3FA supplements since the last trial visit. Participants should be reminded that over-the-counter O3FA supplements are prohibited.
- One box of IMP will be dispensed.

- The IMP dispensed at the previous visit should be checked regarding the expiry date and the participant should be advised to use the IMP box currently in use before opening the IMP box dispensed at the most recent visit.
- See Biospecimen Collection protocol if participant is already in this sub-study. A sample collection pack may need handing /posting to the participant at visit 7.
- If the EMT2 participant has not already taken part in the Biospecimen Collection, an invitation to join the Biospecimen Collection sub-study to provide a single stool and urine sample should be extended to the participant using the dedicated post-surgery PIS/ICF (see Biospecimen Collection protocol).
- If new written informed consent for the Biospecimen Collection sub-study is obtained, a sample collection pack should be provided according to the Biospecimen Collection protocol.

See Section 13.5 for details of remote follow-up for Visits 7-9.

13.8 Visit 10/End of Interventional Phase: Treatment Assessments and Data Collection

Prior to or at Visit 10, all participants (whether they have continued on IMP or not) should be contacted to discuss the possibility of joining the extended follow-up phase of EMT2 and obtain written informed consent to continue into the extended follow-up phase.

Participants will have the visit 10 no later than 48 months (+/- 2 months) after liver resection surgery.

The following assessments will be carried out at the visit:

- Clinical evaluation to assess for disease progression and new primary cancer, as per local standard practice.
- Toxicity assessment: collection of any adverse events which may have occurred since the last trial visit.
- Details of hospital resource activity (e.g. hospital inpatient stays, outpatient clinics attending, accident and emergency attendances).
- Participant self-reported assessments: the EQ-5D, EORTC QLQ-C30 and QLQ-LMC21 Quality of Life questionnaires and a health economics questionnaire will be administered to the participant in a Participant Questionnaire Visit 3-10 Pack. Questionnaires should be completed by participants at the time of clinical assessment, but before discussion of the outcome of any medical assessments or blood tests wherever possible.

- Weight in kilograms (in light indoor clothing and without shoes).
- CT scan of thorax, abdomen and pelvis.
- Treatment compliance: the participant will be asked if they have missed any treatment doses since the last trial visit and for what reason.
- Details of concomitant medications including over-the-counter O3FA supplements since the last trial visit.
- The IMP dispensed at any previous visit should be returned to pharmacy. For those who have undergone remote follow-up, arrangements will be made for the trial courier to collect all unused IMP.
- See Biospecimen Collection protocol if participant is in this sub-study. A sample collection pack may need handing /posting to the participant at visit 10.

Participants who have completed the intervention phase (whether still taking IMP or not) and have provided separate written informed consent for extended follow-up will continue into the extended follow-up phase.

The extended follow-up phase of the trial consists of annual case record review at 60, 72 and up to a maximum 84 months after the intervention phase ended and will finish two years after the last participant is randomised to the EMT2 trial.

13.9 60 days post-treatment telephone call

Participants will be contacted 60 days after the participant's visit 10 if the participant was still taking IMP at visit 10. The research nurse will contact the participant by telephone to perform the following assessments:

- Toxicity assessment: collection of any adverse events which may have occurred over the last 60 days.
- Details of any 'over-the-counter' O3FA supplement use since the last trial visit.

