Duration	Participants will start treatment before CRCLM surgery and will continue to receive treatment for a minimum of 2 years and a maximum of 4 years post-liver resection. Participants are followed up for 60 days beyond the end of treatment and then by case record review annually to collect primary outcome and overall survival data.
Evaluation of outcome measures	
Participants are clinically assessed 6 months post-operatively (from liver resection) and at 6-monthly intervals thereafter for disease progression/recurrence.
 
QoL outcomes are assessed using the EQ-5D, EORTC QLQ-C30 and QLQ-LMC21 supplementary module questionnaires.
 
Health economic outcomes are assessed using a modified UK Cancer Costs Questionnaire Version 2.0 and data collected at each trial visit and telephone call.
 
Adverse events will be documented during study treatment and follow-up.
 
Measurement of the red blood cell fatty acid content will be performed by liquid chromatography-tandem mass spectrometry (LC-MS/MS) measurement of individual fatty acid (FA) species.
 
Changes in lean body mass will be measured longitudinally from routine CT abdomen images based on muscle area at the L3 vertebral level.

4. Trial Schema

* Full inclusion and exclusion criteria in Section 9

5. Abbreviations and Glossary

Abbreviation	Definition
AA	Arachidonic acid
AE	Adverse Event
ALA	Alpha-linolenic acid
AR	Adverse Reaction
CI	Chief Investigator
COX	Cyclooxygenase enzymes
CRC	Colorectal cancer
CRCLM	Colorectal cancer liver metastasis
CRF	Case Report Form
CT	Computerised tomography
CTRU	Clinical Trials Research Unit
DCIS	Ductal carcinoma in situ
DHA	Docosahexaenoic acid
DFS	Disease-free survival
DMEC	Data Monitoring and Ethics Committee
DPA	Docosapentaenoic acid
EDTA	Ethylenediaminetetraacetic acid
EPA	Eicosapentaenoic acid
EPA-EE	Eicosapentaenoic acid ethyl ester
EPA-FFA	Eicosapentaenoic acid free fatty acid
EPA-TG	Eicosapentaenoic acid triglyceride
GCP	Good clinical practice
HR	Hazard ratio
IB	Investigator brochure
ICT	Institute of Cancer Therapeutics
IMP	Investigational medicinal product
IPE	Icosapent ethyl
ITT	Intention to treat
LC-MS/MS	Liquid chromatography-tandem mass spectrometry
MDT	Multi-disciplinary team

MHRA	Medicines and Healthcare products Regulatory Agency
NOAC	New oral anticoagulant
O3FA	Omega-3 fatty acid
O6FA	Omega-6 fatty acid
OS	Overall survival
PFS	Progression-free survival
PG	Prostaglandin
PI	Principal Investigator

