12.2 Treatment Regimen

Participants will be randomised to receive either 4 x 1g capsules of IPE or 4 identical placebo capsules daily. Participants should take their capsules with food.

The trial treatment should be taken daily from the date of randomisation until the participant has completed study treatment (maximum of four years treatment post liver resection).

Trial treatment will continue following diagnosis of disease progression or diagnosis of a new primary cancer as there is still potential for EPA treatment to improve outcomes of any new or recurrent cancer.

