13.18 Adverse Events and Serious Adverse Events

Adverse Events (AEs) and Adverse Reactions (ARs) will be collected at all trial clinic visits and by 2-weekly telephone calls between visit 1 and visit 2 and at 60 days post visit 10/exit visit. AEs and ARs will be collected on the CRFs. These should be reported via the standard data management routes and expedited reporting is not required.

Serious Adverse Events (SAEs), Serious Adverse Reactions (SARs) and Suspected Unexpected Serious Adverse Reactions (SUSARs) will be collected from randomisation until 60 days after the last trial IMP was taken.

For all SAEs, SARs and SUSARs occurring in the trial, an SAE or SAR Report CRF must be completed and faxed or sent via secure email to the CTRU **within 24 hours** of the site becoming aware of the event (see Pharmacovigilance Section 14).

Please see Appendix B for details on the Pharmacovigilance reporting procedures.

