13.20 Deaths

All deaths occurring from the date of randomisation to the telephone call 60 days after the end of trial treatment must be recorded on the Notification of Death CRF and faxed or sent via secure email to the CTRU **within 24 hours** of the site becoming aware of the death.

Deaths occurring more than 60 days after the end of trial treatment but during trial follow-up must also be recorded on the Notification of Death CRF but may be returned as per standard data management processes.

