14.3.1 Reporting of Adverse Events (AEs)

All AEs occurring **from randomisation up to 60 days after the end of trial treatment** must be recorded on the appropriate CRF. These are not subject to expedited reporting to CTRU.

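### The 60-day safety call hangs on Visit 10 and on still taking IMP, while the safety windows run from the end of treatment, leaving a small gap in adverse event collection

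*Protocol*

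**What the plan says.** The protocol describes the end of safety follow-up in two ways.

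**Anchored to Visit 10.**
- Section 13.9: "Participants will be contacted 60 days after the participant's visit 10 if the participant was still taking IMP at visit 10". The call collects adverse events over the previous 60 days and any over-the-counter omega-3 use.
- Section 13.18 lists the collection points for adverse events and reactions as all trial visits, then "by 2-weekly telephone calls between visit 1 and visit 2 and at 60 days post visit 10/exit visit". It does not repeat the on-IMP condition.

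**Anchored to the end of treatment, for all participants.**
- Section 3, Trial Summary (Duration): "Participants are followed up for 60 days beyond the end of treatment".
- Section 13.18, serious events: they "will be collected from randomisation until 60 days after the last trial IMP was taken".
- Section 14.3.1, adverse events: "from randomisation up to 60 days after the end of trial treatment". Sections 14.3.2 to 14.3.4 use the same window for reactions and serious events.
- Section 13.20: "All deaths occurring from the date of randomisation to the telephone call 60 days after the end of trial treatment" go on the expedited death form. Section 13.19 closes the pregnancy window at the same call.
- Appendix A heads the telephone column as 60 days after treatment end.

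Two timing statements also bear on the point. Section 13.8: "Participants will have the visit 10 no later than 48 months (+/- 2 months) after liver resection surgery". Section 12.2 has treatment taken daily "until the participant has completed study treatment (maximum of four years treatment post liver resection".

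**The concern.** A site cannot follow all of these passages for a participant who stops before Visit 10. By 13.9 there is no call. By 13.19 and 13.20 there is a call, and it marks the end of a reporting window.

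The protocol provides several routes to an early permanent stop: a persistent adverse event (12.2.4), prohibited omega-3 use (12.2.2), emergency unblinding (12.3.1) and pregnancy (13.19). Safety and tolerability is a stated secondary objective (7.3). How completely events are collected in the last 60 days should not depend on when, or why, someone stopped. The question is how much of the window is left without a planned contact once the rest of the schedule is taken into account.

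**Working it through.** The protocol gives no figure on this point to reproduce. The check sets the passages against each other and adds simple interval arithmetic.

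**Inputs.** Safety window: 60 days after the last dose (13.18, 14.3). Visits: every 6 months, +/- 2 weeks (13.5 to 13.7). Each visit from 3 to 10 collects adverse events since the previous one. Treatment lasts from 2 to 4 years after resection (12.1). One month = 365.25/12 = 30.44 days, so a visit interval is 6 x 30.44 = 182.6 days.

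**Step 1: early stoppers who keep attending.** Sections 12.2.2, 12.2.4, 12.3.1 and 12.4 keep them in follow-up.
- Longest wait from the stop to the next visit: 182.6 + 14 = 196.6 days if that visit is two weeks late. It is 182.6 + 28 = 210.6 days if the previous visit was also two weeks early.
- Lag after the window closes: 196.6 - 60 = 136.6 days, or 210.6 - 60 = 150.6 days.
- If stop times are uniform within an interval (assumption), the next visit falls inside the window for 60/182.6 = 33% of stops. The visit after that then covers the rest of the window.

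So the window is covered for this group, but by recall and up to about five months after it has closed.

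**Step 2: stops within 60 days before Visit 10.** For a stop k days before Visit 10, that visit covers the first k days and leaves 60 - k days. No later contact collects adverse events. Section 13.9 withholds the call, and the extended follow-up in 13.10 and 13.11 collects only progression and new primary cancers.
- A stop the day before Visit 10 leaves 60 - 1 = 59 days.
- If k is uniform on 0 to 60, the average left uncovered is 30 days.
- Share of stop times in this stretch, if uniform up to Visit 10 (assumption): 60/(48 x 30.44) = 4.1% when Visit 10 is at 48 months, and 60/(24 x 30.44) = 8.2% when it is at 24 months.

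**Step 3: dosing ended at the four-year maximum, Visit 10 later.** Visit 10 may fall as late as 48 + 2 = 50 months. Someone who ends dosing at month 48 and attends at month 49 is no longer taking IMP at the visit, so has no call, and 60 - 30.4 = 29.6 days of the window remain. At month 50 the elapsed time is 2 x 30.44 = 60.9 days, so Visit 10 itself covers the window. The uniform model in Step 2 does not represent a cluster of stops at month 48, and the protocol does not allow their number to be estimated.

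**Step 4: participants who stop and decline visits.** Section 12.4 allows this and says that safety data will still be collected after consent for data collection is withdrawn. No contact or record check is scheduled at day 60 for that purpose.

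**The case against.** The strongest reply is that the condition in 13.9 has a sensible reason. A participant whose treatment ends at Visit 10 has no later visit, so needs a call. One who stops earlier has later visits, each with a look-back over the whole interval. Reporting of serious events also does not depend on a call. Serious events and reactions go to the CTRU within 24 hours of site awareness (14.3). Section 14.3.4 extends this to participants who withdrew consent for data collection and to serious reactions learned of after the window. Deaths after day 60 go on the same form by the routine route (13.20), and every pregnancy is followed to its outcome (13.19). Someone who declines visits may decline a call as well.

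Most of this stands. A reader might infer from 13.9 that early stoppers, including those who stop because of harm, leave safety follow-up. The protocol says otherwise. A reader might also multiply an assumed stopping rate by the sample size. That would count calls not made, not events lost, and the 15% dropout in 18.1.1 is a sample-size allowance, not a rate of permanent IMP cessation.

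The reply does not remove the contradiction between 13.9 and sections 13.19, 13.20 and Appendix A. Nor does it reach Steps 2 and 3, where no later visit exists to look back. For those who decline visits, 13.9 is not the cause, but the protocol still promises safety data without scheduling any means of obtaining them.

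**Conclusion.** The point holds in a limited form. Section 13.9 contradicts the safety windows and the passages that presuppose a call at 60 days after treatment ends. The resulting gap concerns mainly non-serious adverse events, in two groups:

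- participants whose last dose falls within the 60 days before Visit 10, about 4-8% of stoppers, including any who end dosing at the four-year maximum before a later Visit 10;
- participants who stop and decline further visits.

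The 4-8% rests on uniform stop times over 48 or 24 months. The protocol gives no discontinuation rate, so it cannot be turned into a number of participants. For early stoppers who keep attending, the weakness is delay and recall, not absence of data. It may be tempting to conclude that the gap biases the safety comparison towards no difference. The documents give no stopping rates by arm, so no direction of bias can be claimed.

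This is worth correcting because the change is cheap and also removes a contradiction that sites would otherwise resolve differently. It does not threaten the trial's main conclusions.

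**What to change.** - In 13.9, 13.18 and Appendix A, set the call at 60 days after the last IMP dose and remove the condition of still taking IMP at Visit 10. At the least, everyone whose 60-day window runs past their last scheduled visit should be called. A call to every early stopper who still attends visits is desirable but not essential.
- For participants unwilling to attend or be called, make a record check at the same point where consent allows.
- In 13.19 and 13.20, end the windows at day 60 after the last dose instead of at the telephone call.
- Reconcile the Visit 10 window in 13.8 with the treatment maximum in 12.2. Which of the two should change is for the trial team to decide.

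The cost is an amendment to the wording and a few short calls or record checks. The Withdrawal CRF, already due within 24 hours (12.4), can trigger them. Because 12.4 delays that form until it is clear that treatment will not resume, day 60 should be counted from the last dose and not from the form.
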